In 2010, we conducted a retrospective review of 4 cases and found that BLUSA tracheostomy helped facilitate communication in this unique population (IRB #: NA_00041547). Now, we would like to formally conduct a prospective study to evaluate the outcomes of patients using a BLUSA using a pretest-posttest research design.

Identifying the predictors of intelligibility and the impact of BLUSA on Quality of Life (QOL) and communication will promote communication between patients and healthcare providers. This empowers patients and allows healthcare staff to obtain a more accurate assessment of patients’ condition and tailor care accordingly.

2. Objectives (include all primary and secondary objectives)

Specific Aim 1: Determine the impact of a BLUSA on QOL in patients requiring prolonged mechanical ventilation in the hospital

Hypothesis 1a: The mean health-related QOL scores of patients who use BLUSA will be significantly higher compared to patients who do not use BLUSA.

Hypothesis 1b: The mean voice-related QOL scores of patients who use BLUSA will be significantly higher compared to patients who do not use BLUSA.

Specific Aim 2: Determine the outcomes of communication following the use of BLUSA in patients requiring prolonged mechanical ventilation in the hospital.

Hypothesis 2: Effectiveness of communication in patients who use BLUSA will be significantly improved compared to patients who do not use BLUSA.

Research Question 2a: What is the time to speech among patients who are unable to speak using a speaking valve?

Research Question 2b: What is the frequency and duration of speech with use of BLUSA?

Specific Aim 3: Identify the predictors of intelligibility in patients requiring prolonged mechanical ventilation in the hospital.

Hypothesis 3: Several factors such as age, sex, educational level, primary diagnosis, indications for mechanical ventilation, indication for tracheostomy, co-morbidities, and severity of illness will significantly contribute to speech intelligibility in patients requiring prolonged mechanical ventilation in the hospital.

Specific Aim 4: Validate the speech item in the health-related QOL instrument to evaluate speech as a domain of QOL in patients requiring prolonged mechanical ventilation in the hospital

Hypothesis 4: The mean health-related QOL scores will moderately correlate negatively with mean voice-related QOL (VR-QOL) questionnaire (criterion validity).

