3. Background (briefly describe pre-clinical and clinical data, current experience with procedures, drug or device, and any other relevant information to justify the research)

1. Abstract from the prior study (IRB #: NA_00041547) that got accepted for publication in Journal of Medical Speech-Language Pathology:

Purpose: To describe the types of talking tracheostomy tubes available, present four case studies of critically ill patients who used a specialized tracheostomy tube to improve speech, discuss their advantages and disadvantages, propose patient selection criteria, and provide practical recommendations for medical care providers.

Method: Retrospective chart review of patients who underwent tracheostomy in 2010.

Results: Of the 220 patients who received a tracheostomy in 2010, 164 (74.55%) received a percutaneous tracheostomy and 56 (25.45%) received an open tracheostomy. Among the percutaneous tracheostomy patients, speech-language pathologists were consulted on 113 patients, 74 of whom were on a ventilator. Four of these 74 patients received a talking tracheostomy tube, and all four were able to speak successfully while on the mechanical ventilator even though they were unable to tolerate cuff deflation.

Conclusions: Talking tracheostomy tubes allow patients who are unable to tolerate cuff deflation to achieve phonation. Our experience with talking tracheostomy tubes suggests that clinicians should consider their use for patients who cannot tolerate cuff deflation.

2. Additionally, over the last couple of years, the use of BLUSA has increased dramatically at the Johns Hopkins Hospital.

4. Study Procedures

- a. Study design, including the sequence and timing of study procedures (Distinguish research procedures from those that are part of routine care).
Design: Prospective Pretest-Posttest design Clinical Trial – Pilot Study

Sequence and timing:

A. Pre – Assessment

1. Electronic Patient Records (POE, EPR, or EPIC)
 - a. Demographic Data
 - b. Patient Characteristics
 - c. Patient Outcomes
2. Patient Survey
 - a. Quality of life
 - b. Voice-Related quality of life

B. Intervention vs. Control Group

Intervention Group:

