- a) The BLUSA trial involves placement of a BLUSA tracheostomy tube by respiratory therapist after obtaining an order from an authorized prescriber (MD, PA, or NP). The SLP sets up the tracheostomy tube for speech and then determines the optimal air flow required for voicing. This amount of air flow is communicated to the ICU staff for further use.
- b) We will ensure that the SLP meets with the patient for a minimum of 3 sessions within a week to optimize the use of a BLUSA.
 - i. SLP will also assess the duration of successful speech during each session
 - ii. Sentence intelligibility will also be assessed during the 3rd session. This session will be audio-taped and reviewed by a second rater for sentence intelligibility.
 - iii. SLP will determine the level of independence with BLUSA during the 3rd session.

Control Group:

- a) This group will also receive BLUSA trial as standard of care but a week later after the pre and post assessments have been completed

C. Post-Assessment

[figure not shown]
1. Electronic Patient Records (POE, EPR, or EPIC)
 - a. Patient Characteristics
 - i. Severity of Illness
 - b. Patient Outcomes
 - i. Time to BLUSA in days
 - ii. Time between speaking valve trial and BLUSA
2. Patient Survey
 - a. Quality of life
 - b. Voice-Related Quality of life
 - c. Level of independence to use of BLUSA
 - d. Patient satisfaction to use of BLUSA

Setting: All vented units at the Johns Hopkins Hospital (MICU, SICU, CICU, CCU, NCCU, WICU, Wbg 5D, Wbg 5C & MPCU)

Instruments:

Name	Concept measured	Number of items
QOL-MV	Quality of life in mechanically ventilated patients questionnaire	12
VR-QOL	Voice-related quality of life questionnaire	10
SIT	Sentence intelligibility test	11
SOFA	Sequential Organ Failure Assessment Tool	6
RASS	Richmond Agitation Sedation Scale	1
CAM-ICU	Confusion Assessment Method	4
Additional questions	Demographic Data Patient's independence and satisfaction with BLUSA	2

Study Protocol Flow Chart

Date: 12/19/2013

Principal Investigator: [name]

Application Number: NA_00086689

- b. Study duration and number of study visits required of research participants.
The study duration is estimated to be approximately 2 weeks per patient with a total of 5 visits by study team.
- c. Blinding, including justification for blinding or not blinding the trial, if applicable. Patients will not be blinded to intervention or control group.

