 1. Sentence intelligibility
 2. Level of independence with BLUSA
 3. Patient satisfaction with BLUSA
- c) Variables of Interest
 1. Age, Sex, Race
 2. Indication for ICU admission
 3. Indication for Tracheostomy
 4. Severity of Illness (measured by SOFA scores)
 5. Delirium (CAM-ICU)
 6. Sedation (RASS)
 7. Motor Speech (Cranial nerve assessment V, VII, IX, X, and XII)
 8. Information about secretions (suction frequency, secretion quality and quantity)
 9. Time to SLP consult in days
 10. Time to initial in-line speaking valve trial
 11. Severity of Illness
 12. Time to BLUSA in days
 13. Time between speaking valve trial and BLUSA

d) Statistical plan including sample size justification and interim data analysis.

In order to compare changes in health-related quality of life from pre-assessment to post-assessment, we need 73 participants in each group. This allows for a 20% drop out rate and is based on a sample size of 61 individuals in each group to achieve 80% power and a clinically meaningful 20% increase in health-related QOL mean score from 61.16 (SD \pm 21.74) to 73.38 (SD \pm 26.09) based on another "Quality of Life in Mechanically Ventilated Patients" study by PI. We assume a two-tailed test with a significance level of $\alpha = 0.05$.

Interim data analysis will be conducted after 12 months of data collection. Mean, standard deviation, median and inter-quartile range will be calculated for continuous variables. Paired t-tests will be used to compare pre and post assessment scores for continuous variables. Frequencies and percentages will be calculated for categorical variables. Chi square and Fisher Exact tests will be used to compare pre and post assessment scores of categorical variables. Validation of the QOL instrument will include calculation of Cronbach's alpha, Pearson correlation, Kappa.

e) Early stopping rules.

Reasons for stopping data collection for a participant will include

1. change in clinical condition
2. discharge from the hospital

8. Risks

a. Medical risks, listing all procedures, their major and minor risks and expected frequency.

Administration of questionnaires repeatedly can be burdensome. In addition, questions about their quality of life while mechanically ventilated may be emotionally distressing.

b. Steps taken to minimize the risks.

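### The readable text does not say how patients are assigned to immediate or delayed BLUSA, so a between-group QOL difference can reflect who was chosen to go first

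*Combined protocol and SAP*

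**What the plan says.** Section 4a gives the design as "Design: Prospective Pretest-Posttest design Clinical Trial – Pilot Study", and the abstract in Section 1 uses the same label. The sequence in Section 4a is A, pre-assessment; then "B. Intervention vs. Control Group"; then C, post-assessment. Under B, the intervention group has the tube placed "after obtaining an order from an authorized prescriber (MD, PA, or NP"), followed by sessions with the speech-language pathologist. For controls the text reads: "This group will also receive BLUSA trial as standard of care but a week later after the pre and post assessments have been completed". Section 4d repeats the one-week delay.

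Section 4c deals with masking only: "Patients will not be blinded to intervention or control group".

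The claims are comparative. Aim 1 in Section 2 concerns the impact of BLUSA on QOL, and Hypothesis 1a reads "The mean health-related QOL scores of patients who use BLUSA will be significantly higher compared to patients who do not use BLUSA". Hypotheses 1b (voice-related QOL) and 2 (effectiveness of communication) make the same contrast. Section 7 d sizes the study for two groups, "we need 73 participants in each group", and names paired t-tests for continuous variables.

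None of these sections mentions randomisation, sequence generation, concealment, alternation, matching or any other assignment rule.

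**The concern.** A contrast between users and non-users of BLUSA can be read as an effect of the tube only if the two groups would otherwise have fared alike over the study week. Concealed random allocation secures that. A text that names two groups and no method leaves the choice to whoever enrols or treats the patient. The setting gives room for preference: nine units take part, BLUSA is already available as standard care (Section 4d), and the only planned difference between the groups is who gets it first.

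The pre-assessment gives partial protection at best. Comparing changes from baseline removes a stable difference in starting QOL. It does not remove a difference in expected course, for example if patients thought likely to improve that week are placed in the immediate group. Section 7 lists SOFA and other characteristics as variables of interest, but the statistical plan in Section 7 d names no between-group model that adjusts for them or for baseline QOL. Selection on unmeasured prognosis could not be repaired by analysis once patients are enrolled.

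**Working it through.** **1. Does the sample size depend on a two-group contrast?**

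Inputs from Section 7 d: means 61.16 and 73.38, SDs 21.74 and 26.09, two-sided α = 0.05, power 80%, 61 per group.

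- Difference: 73.38 − 61.16 = 12.22.
- Root-mean-square SD: √[(21.74² + 26.09²)/2] = √[(472.63 + 680.69)/2] = 24.01.
- n per group = 2 × (1.960 + 0.842)² × 24.01² / 12.22² = 60.6, rounded up to 61.
- Power at 61 per group: 0.802.

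The stated 61 is reproduced by the formula for two independent means. The plan's own figure therefore presumes a comparison of two separate, comparable groups.

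**2. Where could an assignment rule stand?**

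- Section 1: names the design; no rule.
- Section 2: compares users with non-users; no rule.
- Section 4a A to C: gives the order of steps and what each group receives; no rule.
- Section 4c: masking only.
- Section 7 d: group sizes and tests; no rule.
- Flow chart in Section 4a: not shown in the text available, so not checked.

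**3. What could the gap allow? (Illustration.)**

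Assume no true BLUSA effect, 61 per group, and a comparison of post-assessment scores alone. Let selection move the expected group means apart by f standard deviations. The documents give no value for f, so a range is shown.

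- Standard error in SD units: √(2/61) = 0.181.
- Shift in standard errors: f / 0.181.
- Two-sided rejection rate: P(Z > 1.96 − f/0.181) + P(Z < −1.96 − f/0.181).

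| f (assumed) | Points at SD 24.01 | Share of 12.22 | f / 0.181 | Rejection rate |
|---|---|---|---|---|
| 0 | 0 | 0% | 0 | 5% |
| 0.1 | 2.4 | 20% | 0.55 | 8.6% |
| 0.25 | 6.0 | 49% | 1.38 | 28.2% |
| 0.5 | 12.0 | 98% | 2.76 | 78.9% |

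Because the shift is in SD units, the rates do not depend on which SD is used. With 21.74, a shift of 0.25 SD is 5.4 points (44% of 12.22) and the rate is again 28.2%.

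**4. After the fix.** Concealed 1:1 randomisation sets the expected selection shift to zero and leaves the requirement at 61 evaluable per group.

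**The case against.** The strongest objection is the missing flow chart. A short institutional form may well show the split there, and a figure lost in text extraction is not a gap in the plan. This stands as a limit on the conclusion. A reader might infer that assignment was non-random and unconcealed; the documents do not establish that. They support only the statement that the readable text gives no method. If the flow chart shows randomisation, what remains is to describe sequence generation and concealment if the chart does not.

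A reader might also infer that patients readiest to speak go first while sicker patients, or those on slower units, wait. Nothing written says so. Controls wait because the protocol sets a delay. The prescriber's order is a step in placing the tube, not an allocation rule, and controls who later receive BLUSA would presumably need one too. Section 5 requires every participant to be awake, alert and attempting to communicate, and excludes delirium, which narrows differences in readiness.

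Nor do the documents show that staff see SOFA, sedation or secretion data before groups are formed. The pre-assessment list says only patient characteristics, and listing B after A does not fix when assignment happens or who has seen what. Forming groups after baseline is in any case sound when allocation is concealed.

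The illustration uses post-scores only, whereas Section 7 d speaks of comparing changes. A stable baseline difference would cancel from a change comparison, and only differential change would bias it. That is right, and it is why the percentages are not an estimate of bias in this trial.

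Finally, the study is labelled a pilot. It is nonetheless sized at 80% power for a hypothesis on its primary outcome, so the label does not remove the need for comparable groups.

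**Conclusion.** The point holds in this form: the readable text creates two groups, states between-group hypotheses and sizes the study for a two-group comparison, but gives no method of assignment and names no baseline-adjusted between-group analysis. Followed as written, it permits selective assignment, and a QOL difference could not then be attributed to BLUSA.

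The absence of a rule in the text is certain; what the flow chart contains is not known. The size of any bias is unknown. The rates of about 9%, 28% and 79% rest on assumed selection differences of 0.1, 0.25 and 0.5 SD, no true effect, 61 per group and a post-score-only test. They show sensitivity to selection and do not show that this trial is biased. The matter should be settled before enrolment because later analysis cannot restore comparability on unmeasured prognosis.

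**What to change.** In Section 4a B, state that after consent and a completed pre-assessment each patient is randomised 1:1 to immediate or one-week-delayed BLUSA, from a computer-generated list concealed until the pre-assessment has been entered in the study database. Blocking and stratification by unit are optional. If the flow chart already specifies randomisation, bring it into the text and add how the sequence is generated and concealed.

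If assignment will not be random, state the rule that will be used and reword Aim 1 and Hypotheses 1a, 1b and 2 as associations.

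The cost is a protocol amendment and an allocation list. The delayed control group already exists, so no patients or visits are added and the 61 evaluable per group is unchanged. The small downside is that treating teams lose any choice of who goes first.

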- d. Justification of why participants will not receive routine care or will have current therapy stopped.
If patient is not willing to participate in the study, their routine care will not be altered. They will still have the opportunity to use BLUSA per current standard of care. Patients who are in the control group will also receive BLUSA but a week late.
- e. Justification for inclusion of a placebo or non-treatment group. N/A
- f. Definition of treatment failure or participant removal criteria.
If there is a change in clinical condition that prevents study team from continuing with the BLUSA trial or if the patient is discharged from the hospital, the patient will be dropped from the study.
- g. Description of what happens to participants receiving therapy when study ends or if a participant's participation in the study ends prematurely.
If participants receiving BLUSA complete the study (after the post-assessment), they will continue to use BLUSA per our current standard of care. If the participant's participation using BLUSA ends prematurely due to change in clinical condition, then they will be dropped from the study. But if their condition improves and warrants reuse of BLUSA, they will be offered BLUSA per our standards of care but will not be re-enrolled in the study.

5. Inclusion/Exclusion Criteria

Inclusion Criteria:

Mechanically ventilated via tracheostomy
Awake, alert, and attempting to communicate
Able to understand English

Exclusion Criteria:

Delirium
Fresh tracheostomy within 48 hours
Laryngectomy

6. Drugs/ Substances/ Devices

- a. The rationale for choosing the device to be used.
 - 1. Enables speech in patients who are mechanically ventilated and unable to tolerate cuff deflation.
 - 2. Over the last couple of years, the use of BLUSA has increased dramatically at the Johns Hopkins Hospital.
 - 3. Its impact on quality of life is unknown.
 - 4. This device has the speech attachment that the routine tracheostomy tubes do not have.
 - 5. This device' speech attachment has a wider lumen and is detachable for cleaning.
- b. Justification and safety information if FDA approved drugs will be administered for non-FDA approved indications or if doses or routes of administration or participant populations are changed. N/A
- c. Justification and safety information if non-FDA approved drugs without an IND will be administered. N/A

7. Study Statistics

- a) Primary outcome variables
 1. Quality of life
- b) Secondary outcome variables

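### Before the post-assessment, a prescriber's order for BLUSA is needed only in the intervention group, and a comparison by use lets that step select patients

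*Combined protocol and SAP*

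**What the plan says.** - **The order.** Section 4a, part B, Intervention Group item a, describes the BLUSA trial as "placement of a BLUSA tracheostomy tube by respiratory therapist after obtaining an order from an authorized prescriber (MD, PA, or NP". This comes after the pre-assessment in the listed sequence. The order is mentioned nowhere else in the readable text.
- **Controls.** Section 4a, Control Group: "This group will also receive BLUSA trial as standard of care but a week later after the pre and post assessments have been completed".
- **Eligibility.** Section 5 requires ventilation through a tracheostomy, "Awake, alert, and attempting to communicate", and comprehension of English. It excludes delirium, "Fresh tracheostomy within 48 hours" and laryngectomy. No item asks whether the patient is a candidate for a BLUSA tube. Intolerance of cuff deflation, part of the device rationale in section 6a, is not an entry criterion either.
- **Comparison.** Section 2, Hypothesis 1a: "The mean health-related QOL scores of patients who use BLUSA will be significantly higher compared to patients who do not use BLUSA". Hypotheses 1b and 2 are framed the same way. No analysis by assigned group is stated.
- **Removal.** Section 4f drops a patient on discharge or under this condition: "If there is a change in clinical condition that prevents study team from continuing with the BLUSA trial". Section 7e is broader. Under "Reasons for stopping data collection for a participant will include" it lists a clinical change and discharge, with no limit to one group.
- **Sizing.** Section 7d sizes the study on change in health-related QOL from pre- to post-assessment, with 61 evaluable and 73 enrolled per group.

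**The concern.** A tube cannot be placed without the order, and an order can be withheld. In the intervention group that decision falls before the outcome is measured; in the control group any such decision falls after it. If the order partly reflects how fit the patient is for a tube change, one group passes through a prognostic filter before its outcome and the other does not.

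The filter matters because of how the comparison is worded. An intervention patient without an order is not a BLUSA user, and no text keeps that patient in the intervention group. The nearest written rule, section 4f, removes patients whose BLUSA trial cannot continue, and before the post-assessment a control has no BLUSA trial that could be interrupted. If patients without an order would have had a poorer week, leaving them out of one group only would raise the BLUSA group's mean change for reasons unrelated to speech. At stake is the primary QOL comparison, and the voice-related QOL and communication comparisons with it.

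**Working it through.** **1. The plan's own figure (section 7d).** Target difference: 73.38 − 61.16 = 12.22 points. Combined SD: √[(21.74² + 26.09²)/2] = √576.66 = 24.01. For a two-sided 5% test with 80% power:

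n per group = 2 × 24.01² × (1.960 + 0.842)² / 12.22² = 60.6, rounded up to 61.

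This matches the stated 61, so the sizing treats 12.22 points as a difference between two independent groups. That makes it the right yardstick for a between-group bias.

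**2. Form of the bias.** Suppose a fraction f of intervention patients have no order and are left out of the comparison. Without BLUSA, let the mean QOL change over the week be m₁ in patients who would get an order and m₀ in those who would not. Let the effect in users be E.

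- Users' mean change: m₁ + E
- Controls' mean change, nobody left out: (1 − f)m₁ + f·m₀
- Difference: E + f(m₁ − m₀)

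The bias is f × Δ, with Δ = m₁ − m₀. This is a difference in *change*, not in post-assessment level. A deficit of equal size at both assessments gives Δ = 0.

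**3. Size.** The documents give neither f nor Δ, so every value below is an assumption.

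| f | Δ (points) | Bias (points) | Share of 12.22 |
|---|---|---|---|
| 0 | any | 0 | 0% |
| 10% or 20% | 0 (deficit stable over the week) | 0 | 0% |
| 10% | 5 (half of a 10-point gap already present at baseline) | 0.5 | 4% |
| 20% | 5 | 1.0 | 8% |
| 10% | 10 | 1.0 | 8% |
| 20% | 10 | 2.0 | 16% |

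**4. Analysis by assigned group.** If intervention patients without an order stay in their group and are assessed, that group also contains the fraction f with mean change m₀. The term f(m₁ − m₀) then cancels, whatever f and Δ are.

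**The case against.** The strongest reply is that the documents never call the order a suitability check. Section 4a says who places the tube and on whose authority; it gives no fitness criteria, no route for refusal and no refusal rate. The plan expects controls to receive BLUSA a week later, which suggests that every enrolled patient is regarded as a candidate. The entry criteria screen both groups equally on alertness, delirium and a recent tracheostomy. Section 7e would stop data collection for a deteriorating control as well. No allocation method is given in the readable text and the flow chart is not shown, so the timing of the order relative to assignment is read from the order of the sections.

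All of this stands as a limit on what can be asserted. It does not close the route. Section 7e sets no threshold, and section 4f ties removal to a BLUSA trial that controls have not started. Nothing says how an intervention patient without an order is counted.

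Three stronger readings are tempting, and the documents support none of them:

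- *Users are filtered by fitness and controls are not.* This needs refused patients to be excluded, which is not stated. Controls also come to the same BLUSA trial later, so the asymmetry holds only up to the post-assessment.
- *The bias could not be repaired afterwards.* Baseline QOL and SOFA are collected and would allow partial adjustment. They are not the prescriber's judgement, however, and no adjusted analysis is planned.
- *The bias could reach a third of the target.* A 20-point gap in post-assessment score with f = 20% gives 4 points, or 33%. That is a gap in level, whereas the study is sized on change, so whatever part of it was present at baseline cancels.

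**Conclusion.** The point holds as a selection route that the plan leaves open, not as a demonstrated bias. Three things are in the text: before the post-assessment the order applies to one group only, candidacy is not an entry criterion, and the hypotheses compare by use with no rule that keeps untreated intervention patients in their group. Three things are inferred: that the order acts as a suitability judgement, that it follows assignment, and that patients without one leave the comparison.

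If those inferences are right and patients without an order would change less favourably, the bias favours BLUSA. Under the assumed f of 10-20% and a 10-point difference in change, it is 1 to 2 points, 8-16% of the target. That is modest beside the planned effect, and it is nil if no order is declined, if the deficit is stable over the week, or if patients are analysed as assigned. The change is worth making because it is cheap and does not require anyone to know f or Δ.

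**What to change.** 1. **Section 5, both groups.** Add an inclusion criterion that an authorized prescriber has confirmed, before the pre-assessment and before group assignment, that the patient is a candidate for a BLUSA tube. The clinical judgement stays with the prescriber. The order in section 4a remains the practical step that follows.
2. **Sections 2 and 7d.** Word Hypotheses 1a, 1b and 2 and the primary comparison by assigned group. Obtain the post-assessment from intervention patients who do not receive the tube whenever they can answer, and reconcile sections 4f and 7e with this, so that not starting or not continuing the BLUSA trial does not by itself end outcome collection.

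Both parts are needed. The first makes non-receipt less common and applies the same check to both groups; the second covers patients who are confirmed but still do not receive the tube.

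**Cost.** One inclusion line, reworded hypotheses, a sentence on the analysis population, and a few extra post-assessments. BLUSA is already planned for controls a week later, so their prescriber decision is mostly moved earlier. Patients judged unsuitable are not enrolled, which may slow recruitment. The estimate may be slightly diluted: if 5% of confirmed patients still do not receive the tube and gain nothing (an assumption), a 12.22-point effect in users appears as 0.95 × 12.22 = 11.6 points.

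### Sections 4f, 4g and 7e end QOL data collection on a change in clinical condition without asking whether the patient is still in hospital and able to answer

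*Combined protocol and SAP*

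**What the plan says.** Three sections of the combined protocol and SAP govern removal.

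- **4f (leaving the study):** the first ground for dropping a patient reads: "If there is a change in clinical condition that prevents study team from continuing with the BLUSA trial". Discharge is the second.
- **4g (premature end):** if a patient's "participation using BLUSA ends prematurely due to change in clinical condition, then they will be dropped from the study". If the condition later improves, "they will be offered BLUSA per our standards of care but will not be re-enrolled in the study".
- **7e (early stopping rules):** "Reasons for stopping data collection for a participant will include" two items, a change in clinical condition and hospital discharge. The first is neither defined nor tied to BLUSA use.

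The sole primary outcome (7a) is quality of life, taken from the patient survey at pre- and post-assessment (4a). Aim 1 is to "Determine the impact of a BLUSA on QOL in patients requiring prolonged mechanical ventilation in the hospital". For the analysis, 7d states: "Paired t-tests will be used to compare pre and post assessment scores for continuous variables". The only provision for losses is in the sample size: "This allows for a 20% drop out rate and is based on a sample size of 61 individuals in each group". On controls, 4a says: "This group will also receive BLUSA trial as standard of care but a week later after the pre and post assessments have been completed".

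**The concern.** QOL in this study is self-reported, so the natural reason to stop collecting it is that the patient has gone or cannot answer. The plan uses a different trigger. Discharge is listed separately in both 4f and 7e, so the clinical-change trigger reaches patients who are still on the ward. Some of them will be unable to respond, but the rule does not sort them on that basis. The no-return clause in 4g shows this most clearly: a patient well enough to use BLUSA again before the scheduled post-assessment would still go unmeasured.

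Two things are at stake. The first is whom the primary result describes. Changes in condition are foreseeable during prolonged ventilation, and a larger sample does not bring back the patients removed. The second is the comparison in Hypotheses 1a and 1b. 4f and 4g refer to continuing or ending BLUSA use, while controls have no BLUSA until after their post-assessment. Staff could therefore apply an undefined trigger differently in the two groups.

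**Working it through.** **The clauses side by side**

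| Section | Trigger | Tied to BLUSA use? | Asks if able to answer? |
|---|---|---|---|
| 4f | Clinical change that prevents the BLUSA trial; discharge | Yes | No |
| 4g | BLUSA use ends early through clinical change; no re-enrolment | Yes | No |
| 7e | Change in clinical condition; discharge | No | No |

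A patient whose condition changes but who continues BLUSA stays in under 4f and 4g, yet loses data collection under 7e read literally. No readable passage seeks a post-assessment after removal, and a paired test cannot use a patient without a post score.

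**The plan's own figure.** Inputs from 7d: means 61.16 and 73.38 (difference 12.22), SDs 21.74 and 26.09, two-sided 0.05, 80% power.

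- n = (1.96 + 0.8416)² × (21.74² + 26.09²) / 12.22² = 60.6, so 61 per group. The stated figure reproduces.
- Standard error of a difference at 61 per group: √((21.74² + 26.09²)/61) = 4.35 points.

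**Illustration of bias.** Losses by group and score gaps are assumptions; the documents give neither. Let p be the share removed in a group and g the number of points by which removed patients would have scored below those measured. The measured mean then exceeds the mean of all patients by p × g, and the BLUSA-minus-control difference shifts by (pB − pC) × g.

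| Loss, BLUSA v control | g = 10 | g = 20 |
|---|---|---|
| 20% v 20% | 0 | 0 |
| 20% v 10% | +1.0 | +2.0 |
| 10% v 20% | −1.0 | −2.0 |

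- The +1 to +2 points are 8% to 16% of 12.22, or 0.23 to 0.46 of the standard error of 4.35.
- If half of the gap is already present at baseline, change scores shift by 0.5 to 1.0 point (4% to 8% of 12.22).
- If the removed patients are improvers who would have scored higher, g is negative and every non-zero sign flips.

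**What the fix could recover.** Let f be the share of removed patients who respond and gr their gap. The remaining shift per group is p·g − p·f·gr/(1 − p + p·f).

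- f = 0.5, gr = g = 10: 0.889 at p = 0.20 minus 0.474 at p = 0.10 gives 0.42. With g = 20 it is 0.83. About 58% is recovered.
- f = 0.5, gr = g/2: 0.71 and 1.42. About 29% is recovered.
- Discharged patients cannot be recovered and so lower f. With f = 0.25 and gr = g = 10: 1.412 − 0.730 = 0.68, or 32% recovered.

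**The case against.** The strongest reply is that 7e repeats the two reasons in 4f, in the same order, and is probably shorthand for it. On that reading only patients who cannot continue BLUSA leave. Entry requires being awake, alert, attempting to communicate and free of delirium, so a change that stops a speech device may often be a loss of the ability to answer. The re-enrolment bar may simply prevent counting a patient twice. Hypotheses 1a and 1b concern patients who use BLUSA, the design is labelled a pilot, and no readable passage describes random allocation that an all-enrolled analysis would protect. The study flow chart is not shown and may say more.

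Much of this stands. The number of removed patients who could answer is unknown, and the bias figures are small and assumed. A further point also stands: a change may be weaning from the ventilator while still in hospital, and QOL-MV is an instrument for ventilated patients, so a weaned patient's score needs separate handling.

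Three stronger readings are tempting, and the documents do not support them:

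- *The results describe only patients who stayed stable.* That is literal only under 7e.
- *The rules remove BLUSA patients only and so favour BLUSA.* 7e applies to any participant, and a change can be an improvement. Unequal loss is possible but not built in.
- *The removal rule leaves the trial short of its 61.* At 20% loss, 73 leaves 58 (73 × 0.8 = 58.4). That happens because 61 was multiplied by 1.2 (73.2) instead of divided by 0.8 (76.25, so 77). It would arise at 20% loss from any cause. It is a separate sample-size matter and not evidence for this point.

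The reply does not remove the core: none of the three sections makes inability to answer the criterion, and they differ in scope.

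**Conclusion.** The point holds in limited form. As written, the plan stops primary-outcome collection for some inpatients who could still provide it, and the paired analysis then omits them. Patients who stop BLUSA for another reason, such as preference, are not removed by these clauses and are outside this point.

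How many scores would be lost, and which way the comparison would move, cannot be derived from the documents. The 1 to 2 points (0.5 to 1 on change scores) rest wholly on assumed losses and gaps, and show scale only. This should be corrected before data collection, because scores not collected cannot be restored at analysis, but it does not by itself undermine the trial. Confidence is medium: the share of removed patients able to answer is unknown, and the flow chart could not be read.

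**What to change.** - Reconcile 4f, 4g and 7e so that a change in condition, or the end of BLUSA use, does not by itself end data collection.
- Seek the scheduled post-assessment QOL-MV and VR-QOL from every enrolled patient, in either group, who is still in hospital, willing and able to respond. Judge ability with RASS and CAM-ICU, which are already study instruments.
- Use the same reasons for ending data collection in both groups: discharge, death, withdrawal, unable to respond.
- Record ventilation status at the post-assessment.
- Analyse these patients in the group they entered. Add two sensitivity analyses: one limited to patients who continued BLUSA, with controls, which keeps the wording of Hypotheses 1a and 1b; and one limited to patients still ventilated, because of the scope of QOL-MV.
- Report losses by group and reason.

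This concerns data collection only and changes no clinical management.

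**Cost.** A short amendment, using a visit and questionnaires already planned. At the plan's 20% loss (0.20 × 73 = 14.6) it means at most about 15 more post-assessments per group, and fewer in practice. RASS (1 item) and CAM-ICU (4 items) may need recording once more. Section 8a acknowledges that questionnaires can be burdensome and distressing, and recently unstable patients would bear some of that; the pause-or-stop rule in 8b applies. The estimated effect may turn out smaller. Recovery is partial, because discharged patients and those unable to respond stay missing.
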